4.3 SECONDARY ENDPOINTS ANALYSES

All the secondary endpoints will be compared between obinutuzumab (combined treatment groups) and placebo groups. Proportions by treatment groups will be presented for binary endpoints along with difference in proportions between treatment groups, two-sided 95% CI for the difference and p-value.

Estimand attributes for the binary secondary endpoints are defined as follows unless otherwise specified:

- Population: patients with active or active/chronic ISN/RPS 2003 Class III or IV proliferative lupus nephritis.
- Endpoint (variable): Binary secondary endpoint of interest. Patients will be considered non-responder if rescue therapy, treatment failure, death, or early study withdrawal prior to endpoint assessment occur.
- Treatments:

Experimental: Obinutuzumab 1000 mg IV infusion at Day 1 and Weeks 2, 24, 26, and either Weeks 50 and 52 or Week 52 only

Control: Placebo

- Intercurrent events: Rescue therapy, treatment failure, study treatment
 discontinuation, death, or early study withdrawal prior to endpoint assessment.
 Rescue therapy, treatment failure, death and early study withdrawal are addressed
 in the endpoint (variable) definition and are handled under the composite strategy.
 Study treatment discontinuation will be handled using treatment policy strategy.
- Summary measure: Difference in proportions at a specified visit of interest

Intercurrent events described in Section 4.2.1.1 will be handled in the same approach as the primary endpoint unless otherwise specified. Missing data imputation will be similar to the primary endpoint and discussed in the next sections for each of the binary endpoint.

The continuous endpoints (change from baseline) will be summarized using descriptive statistics. A 95% CI of adjusted mean difference between the treatment groups (combined obinutuzumab vs placebo) will be presented along with a p-value. Estimand attributes for the continuous secondary endpoints are defined as follows:

- Population: patients with active or active/chronic ISN/RPS 2003 Class III or IV proliferative LN
- Endpoint (variable): Change from baseline for the variable of interest
- Treatments:

Experimental: Obinutuzumab 1000 mg IV infusion at Day 1 and Weeks 2, 24, 26, and either Weeks 50 and 52 or Week 52 only

Control: Placebo

- Intercurrent events: Rescue therapy, treatment failure, study treatment discontinuation, or death prior to endpoint assessment. Rescue therapy, treatment failure and study treatment discontinuation will be handled using treatment policy strategy.
 - Death will be handled using composite strategy. Data after death will be imputed by a pre-specified single fixed value specified in the next sections for each of the continuous endpoints.
- Summary measure: Difference in adjusted means at a specified visit of interest

The intercurrent events are described in Section 4.2.1.1.

4.3.1 Key Secondary Endpoints

4.3.1.1 Proportion of Patients who Achieve a Proteinuric Response at Week 76

The proportion of patients who achieve a proteinuric response at Week 76 will be analyzed using a CMH test with region and race as stratification factors. Proteinuric response is defined as achievement of all of the following:

- UPCR < 0.8
- No occurrence of the following intercurrent events:
 - Rescue therapy, treatment failure, death, or early study withdrawal

Missing data: Data obtained from the central laboratory only will be used. UPCR will be imputed by multiple imputations using the model specified in Section 4.2.2. The same imputed datasets produced during the analysis of CRR will be used for the analysis of proteinuric response. The analysis will follow the same methods described in Section 4.2.2.

4.3.1.2 Proportion of Patients who Achieve CRR with Successful Prednisone Taper at Week 76

The proportion of patients who achieve CRR with successful prednisone taper at Week 76 is defined as achievement of CRR (defined as Section 4.2.1) at Week 76 with the following:

 No receipt of prednisone >7.5 mg/day (or equivalent) from Week 64 through Week 76

The endpoint will be analyzed using a CMH test with region and race as stratification factors.

Only oral corticosteroid will be considered for evaluating the no receipt of prednisone >7.5 mg/day (or equivalent) criteria and converted to prednisone equivalent dose when applicable.

Data Handling for Oral Corticosteroids

The study team will monitor oral corticosteroids on an ongoing basis for data quality and to ensure all dose adjustments are being correctly captured. All efforts will be made to resolve missing or ambiguous data prior to database lock. In the case that data queries cannot be resolved, data will be handled in a conservative manner as described in the sections below.

The intervals for each dose of oral corticosteroid captured during the taper are expected to be continuous and non-overlapping. Patients who are adequately controlled by their blinded treatment may discontinue oral corticosteroids altogether, but may re-start treatment as required to treat any increases in disease activity. With this in mind, the use of available data will be maximized and incorporated into the imputation of missing or partial dates as follows:

Missing Term	Imputation Method
Start Date	
Missing Day	Latest of the following:
	Previous End Date+1
	First day of the month
Missing Month/Year	Previous End Date+1
End Date	
Missing Day	Earliest of the following:
	Next Start Date-1
	Last day of the month
Missing Month/Year	Next Start Date-1

Within two consecutive dosing intervals, if the end date of the first dose interval is missing or partially missing and the start date of the second dose interval is missing or partially missing, a midpoint approach using the start date of the first interval and the end date of the second interval will be used to assign a cut-off end date, providing these dates are available.

A missing or 'ongoing' final end date will be imputed with clinical cutoff date (CCOD) or the date of withdrawal from the study in case a patient withdraw early from the study. A missing initial start date will be imputed with Day 1 providing the end date is after Day 1, otherwise no imputation will be made.

If there is a start and/or end date, but the total daily dose is missing then the dose will be imputed using the dose from the previous dose.

In the event of overlapping dose intervals, the patient will be assumed to be taking the higher dose for the maximum amount of time possible such that the total daily dose will never be double counted.

Missing UPCR and eGFR Data

Missing UPCR and eGFR data will be imputed by multiple imputations using the model specified in Section 4.2.2. The same imputed datasets produced during the analysis of CRR (described in Section 4.2.2) will be used for this analysis. The CRR with successful prednisone taper at Week 76 will be derived for each datasets. The analysis will follow the same methods described in Section 4.2.2.

4.3.1.3 Proportion of Patients who Achieve an ORR, Defined as Achievement of Either CRR or PRR, Evaluated at Week 50

The proportion of patients who achieve an ORR, defined as achievement of either CRR or PRR, evaluated at Week 50 will be analyzed using a CMH test with region and race as stratification factors. The definition of CRR is explained in Section 4.2.1. PRR is defined as achievement of all of the following:

- ≥50% reduction in UPCR from baseline
- UPCR <1 (or <3 if the baseline UPCR was ≥3)
- eGFR ≥85% of baseline, as calculated using the CKD-EPI equation
- No occurrence of the following intercurrent events:
 - Rescue therapy, treatment failure, death, or early study withdrawal

Intercurrent events are described in Section 4.2.1.1.

Missing data: Data obtained from the central laboratory only will be used.

Multiple imputations will be used for the missing data imputation using the model specified in Section 4.2.2. The analysis will follow the same methods described in Section 4.2.2.

4.3.1.4 Proportion of Patients who Experience Death or Renal-related Events through Week 76

Proportion of patients who experience death or renal-related events through Week 76, defined as the proportion of patients with one or more of the following events:

- Death
- Treatment failure (see Section 4.2.1.1)
- Worsening proteinuria, defined as a confirmed ≥ 50% increase in UPCR to a value ≥3
- Worsening eGFR, define as a confirmed ≥30% decrease in eGFR to a value <60

Worsening proteinuria and eGFR criteria will be evaluated by calculating the specified increase or decrease from the previous visit.

The death or renal related event will occur if any of the above events occur at any visit through Week 76. The proportion of patients who experience death or renal-related

events through Week 76 will be analyzed using a CMH test with region and race as stratification factors.

Estimand attributes for the endpoint are defined as follows:

- Population: patients with active or active/chronic ISN/RPS 2003 Class III or IV proliferative LN.
- Endpoint (variable): Death or renal-related events as defined above.
- Treatments:

Experimental: Obinutuzumab 1000 mg IV infusion at Day 1 and Weeks 2, 24, 26, and either Weeks 50 and 52 or Week 52 only

Control: Placebo

- Intercurrent events: Early study withdrawal prior to Week 76 due to lack of efficacy.
 It will be handled using composite strategy. That is, the early study withdrawals due to lack of efficacy will be considered as events.
- Summary measure: Difference in proportions at Week 76

Early study withdrawals due to reasons other than lack of efficacy will be considered as having missing data.

The missing UPCR and eGFR values will be imputed by the multiple imputation model specified for the primary endpoint in Section 4.2.2 using data from the patients who did not experience death, treatment failure or early study withdrawal due to lack of efficacy.

The death or renal related event endpoint for patients who withdrew early from the study for reasons other than lack of efficacy will then be evaluated based on only the following criteria using the imputed UPCR and eGFR values:

- Worsening proteinuria, defined as a confirmed ≥50% increase in UPCR to a value ≥3
- Worsening eGFR, define as a confirmed ≥30% decrease in eGFR to a value <60

The death or treatment failure will not be imputed.

Worsening proteinuria will be assessed based on 24-hour UPCR which is collected at Week 24, 50 and 76 as per the protocol.

Imputation of eGFR will be made only for the Weeks 24, 36, 50, 64, and 76 as these visits are included in the imputation model (Section 4.2.2). If eGFR values worsened at other missing visits (Weeks 2, 4, 12, 26, and 52) that are not imputed, the worsening due to disease activity should be captured at the next observed or imputed visits. Study withdrawals who have not achieved the event following imputation of their UPCR or eGFR data will be assumed to have not had the event.

The multiple imputation parameters, analysis and pooling steps will be similar to the methods specified in the Section 4.2.2.

4.3.1.5 Mean Change in eGFR from Baseline to Week 76

Change in eGFR from baseline at Week 76 will be analyzed using Analysis of Covariance (ANCOVA) model. The response variable in the model will be change in eGFR from baseline at Week 76. Treatment group (combined obinutuzumab vs. placebo), baseline eGFR and the stratification factors race and region will be included in the model as independent variables. The adjusted difference between the treatment group with 95% CI and p-value will be presented.

The eGFR values for patients who died will be imputed with 0 (composite strategy). All other intercurrent events (specified in Section 4.3) will be handled using treatment policy strategy.

Missing data will be imputed by multiple imputations using FCS predicted mean matching method. A set of candidate donors with 5 members is chosen for the predictive mean matching method. Only patients who did not experience death will be included in the imputation model. Separate imputation models will be used for each treatment group.

The models will contain the following variables (in order of being imputed):

- Baseline eGFR
- Log-serum Albumin at Baseline
- Region (stratification factor)
- Race (stratification factor)
- Sex
- Age
- BMI
- Week 24 eGFR
- Week 36 eGFR
- Week 50 eGFR
- Week 64 eGFR
- Log-serum Albumin at Week 76
- Week 76 eGFR

The imputation will be implemented using the following three standard steps to generate inference from the imputed data. The number of imputations will be set of 100.

1. Imputation step:

- The missing data will be imputed 100 times to generate 100 imputed datasets for the patients who did not experience death.
- Patients who experienced death will be added in each of the datasets to obtain full datasets including all the patients in the analysis population.
- A number of burn-in iterations of 100 and a seed of 5678234 will be used.
- Analysis step: Each of the 100 imputed datasets will be analyzed using ANCOVA model
- 3. **Pooling step:** The results from the 100 imputed datasets will be combined for inference following the methodology developed by Rubin (Rubin 1987).

4.3.1.6 Change in FACIT-F scale from Baseline to Week 76

Change in FACIT-F scale from baseline at Week 76 will be analyzed using ANCOVA model. The response variable in the model will be change in FACIT-F scale from baseline at Week 76. Treatment group, baseline FACIT-F scale and the stratification factors race and region will be included in the model as independent variables. The adjusted difference between the treatment group with 95% CI and p-value will be presented.

The FACIT-F scale for patients who died will be imputed with 0 (composite strategy). All other intercurrent events (specified in Section 4.3) will be handled using treatment policy strategy.

Missing data will be imputed by multiple imputations. Only patients who did not experience death will be included in the imputation model. Multiple imputation methods will be the same as described in Section 4.3.1.5.

The multiple imputation models will contain the following variables (in order of being imputed):

- Baseline FACIT-F score
- Region (stratification factor)
- Race (stratification factor)
- Sex
- Age
- Week 24 FACIT-F score
- Week 50 FACIT-F score
- Week 76 FACIT-F score

4.3.2 Supportive Secondary Endpoints

4.3.2.1 Change in Anti-dsDNA Titer from Baseline to Week 50

Change in anti-dsDNA from baseline at Week 50 will be analyzed with ANCOVA model using the same methods described in Section 4.3.1.5. Anti-dsDNA data will be log-transformed before analyzing. The response variable in the model will be change in log-transformed anti-dsDNA from baseline. Treatment group, baseline log-transformed anti-dsDNA and the stratification factors race and region will be included in the model as independent variables. The adjusted difference between the treatment group with 95% CI and p-value will be presented.

The anti-dsDNA values for patients who died will be imputed with upper limit of quantification (ULOQ, 890 IU/mL) of the analytical method used. All other intercurrent events (specified in Section 4.3) will be handled using treatment policy strategy.

Missing data will be imputed by multiple imputations using the same methods described in Section 4.3.1.5.

The models will contain the following variables (in order of being imputed):

- Baseline log-anti-dsDNA
- Region (stratification factor)
- Race (stratification factor)
- Sex
- Age
- Week 4 log-anti-dsDNA
- Week 12 log-anti-dsDNA
- Week 24 log-anti-dsDNA
- Week 50 log-anti-dsDNA
- Week 76 log-anti-dsDNA

Inclusion of Week 76 value in the model has minimal impact on the Week 50 imputation. The Week 76 anti-dsDNA has been added in the imputation model to facilitate the imputation and analysis of anti-dsDNA at Week 76 which is an exploratory endpoint. Also, to facilitate the analysis of anti-dsDNA at other visits, patients who experienced death will be included in the imputation model, but imputed values after death will be replaced by the ULOQ.

4.3.2.2 Change in C3 from Baseline to Week 50

Change in C3 from baseline at Week 50 will be analyzed using the same method described in Section 4.3.2.1. The response variable in the model will be change in C3 from baseline. Treatment group, baseline C3 and the stratification factors race and region will be included in the model as independent variables.

The C3 values for patients who died will be imputed with LLOQ/2 where LLOQ being the lower limit of quantification. The LLOQ at the central lab is set for C3 at 0.100 g/L. All other intercurrent events (specified in Section 4.3) will be handled using treatment policy strategy.

Missing data will be imputed by multiple imputations using the same methods described in Section 4.3.1.5.

The multiple imputation models will contain the following variables (in order of being imputed):

- Baseline C3
- Region (stratification factor)
- Race (stratification factor)
- Sex
- Age
- Week 4 C3
- Week 12 C3
- Week 24 C3
- Week 50 C3
- Week 76 C3

Inclusion of Week 76 value in the model has minimal impact on the Week 50 imputation. The Week 76 C3 has been added in the imputation model to facilitate the imputation and analysis of C3 at Week 76 which is an exploratory endpoint. Also, to facilitate the analysis of C3 at other visit, patients who experienced death will be included in the imputation model, but imputed values after death will be replaced by the LLOQ/2.

4.3.2.3 Change in SLEDAI-2K from Baseline to Week 76

Change in SLEDAI-2K score from baseline at Week 76 will be analyzed using the same methods as described in Section 4.3.1.5 and Section 4.3.1.

The SLEDAI-2K for patients who died will be imputed with 105 which is the maximum possible SLEDAI-2K value. All other intercurrent events (specified in Section 4.3) will be handled using treatment policy strategy.

The multiple imputation models will contain the following variables (in order of being imputed):

- Baseline SLEDAI-2K
- Region (stratification factor)
- Race (stratification factor)

- Sex
- Age
- Week 24 SLEDAI-2K
- Week 50 SLEDAI-2K
- Week 76 SLEDAI-2K

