2.1 EFFICACY OBJECTIVES

2.1.1 Primary Efficacy Objective

The primary efficacy objective for this study is to evaluate the efficacy of obinutuzumab (combined treatment groups) compared with placebo on the basis of the following endpoint:

- Proportion of patients who achieve a complete renal response (CRR) at Week 76
 CRR is defined as achievement of all of the following:
 - Urinary protein-to-creatinine ratio (UPCR) < 0.5 g/g
 - Estimated glomerular filtration rate (eGFR) ≥ 85% of baseline, as calculated using the Chronic Kidney Disease Epidemiology Collaboration (CKD-EPI) equation
 - No occurrence of the following intercurrent events:
 - Rescue therapy, treatment failure, death or early study withdrawal

2.1.2 Secondary Efficacy Objective

The secondary efficacy objective for this study is to evaluate the efficacy of obinutuzumab (combined treatment groups) compared with placebo on the basis of the following endpoints.

Key Secondary Endpoints

- Proportion of patients who achieve a proteinuric response at Week 76
 Proteinuric response is defined as achievement of all of the following:
 - UPCR < 0.8 g/g
 - No occurrence of the following intercurrent events:
 - Rescue therapy, treatment failure, death or early study withdrawal
- Proportion of patients who achieve CRR with successful prednisone taper at Week 76, defined as achievement of CRR (as above) at Week 76 with the following:
 - No receipt of prednisone > 7.5 mg/day (or equivalent) from Week 64 through Week 76
- Proportion of patients who achieve an overall renal response (ORR), defined as achievement of either CRR or partial renal response (PRR), evaluated at Week 50 PRR is defined as achievement of all of the following:
 - ≥50% reduction in UPCR from baseline
 - UPCR <1 g/g (or <3 g/g if the baseline UPCR was ≥3 g/g)
 - eGFR ≥ 85% of baseline, as calculated using the CKD-EPI equation
 - No occurrence of the following intercurrent events:
 - Rescue therapy, treatment failure, death or early study withdrawal
- Proportion of patients who experience death or renal-related events through Week 76, defined as the proportion of patients with one or more of the following events:
 - Death
 - Treatment failure (see Section 4.4.4.2)
 - Worsening proteinuria, defined as a confirmed ≥ 50% increase in UPCR to a value ≥ 3
 - Worsening eGFR, define as a confirmed ≥ 30% decrease in eGFR to a value < 60
- Mean change in eGFR from baseline to Week 76

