6.3.2.1 Key Secondary Efficacy Endpoints

The estimand attributes for each key secondary endpoint and missing data handling strategies will be documented in the SAP. The key secondary efficacy endpoints are the following:

- Proportion of patients who achieve a proteinuric response at Week 76
 Proteinuric response is defined as achievement of all of the following:
 - UPCR < 0.8 g/g
 - No occurrence of the following intercurrent events:
 - Rescue therapy, treatment failure, death or early study withdrawal
- Proportion of patients who achieve CRR with successful prednisone taper at Week 76, defined as achievement of CRR (as above) at Week 76 with the following:
 - No receipt of prednisone > 7.5 mg/day (or equivalent) from Week 64 through Week 76
- Proportion of patients who achieve an ORR, defined as achievement of either CRR or PRR, evaluated at Week 50

PRR is defined as achievement of all of the following:

- ≥50% reduction in UPCR from baseline
- UPCR<1 (or <3 if the baseline UPCR was \geq 3)
- eGFR≥85% of baseline, as calculated using the CKD-EPI equation
- No occurrence of the following intercurrent events:
 - Rescue therapy, treatment failure, *death* or early study withdrawal
- Proportion of patients who experience death or renal-related events through Week 76, defined as the proportion of patients with one or more of the following events:
 - Death
 - Treatment failure (see Section 4.4.4.2)
 - Worsening proteinuria, defined as a confirmed ≥ 50% increase in UPCR to a value ≥ 3
 - Worsening eGFR, define as a confirmed ≥ 30% decrease in eGFR to a value < 60
- Mean change in eGFR from baseline to Week 76
- Change in FACIT-F scale from baseline to Week 76

All the key secondary endpoints will be compared between obinutuzumab (combined treatment groups) and placebo groups. Proteinuric response, ORR and death or renal-related event will be analyzed similarly as the primary endpoint using a CMH test. Change from baseline in eGFR and FACIT-F scale will be analyzed by appropriate methods derived from estimand attributes and will be specified in the SAP.

To control for multiple comparisons, the primary and key secondary endpoints will be tested in a pre-specified order at a two-sided 0.05 significance level. The order of testing *and multiplicity control method* will be pre-specified in the SAP and finalized prior to database lock for the primary analysis.

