4.2 PRIMARY ENDPOINT(S) ANALYSIS

4.2.1 Definition of Primary Endpoint

The primary estimand attributes are as follows:

- Population: Patients with active or active/chronic ISN/RPS 2003 Class III or IV proliferative lupus nephritis
- Endpoint (variable): CRR. A patient will be considered a responder for CRR if the following conditions are met at the Week 76 visit:
 - UPCR < 0.5
 - eGFR ≥85% of baseline, as calculated using the CKD-EPI equation
 - No occurrence of rescue therapy, treatment failure, death, or early study withdrawal.

Treatments:

- Experimental: Obinutuzumab 1000 mg IV infusion at Day 1 and Weeks 2, 24,
 26, and either Weeks 50 and 52 or Week 52 only
- Control: Placebo
- Intercurrent events: rescue therapy, treatment failure, study treatment discontinuation, death, or early study withdrawal prior to Week 76 (refer to Section 4.2.1.1).

Rescue therapy, treatment failure, death and early study withdrawal are addressed in the endpoint definition and are handled under the composite strategy.

Study treatment discontinuation will be handled using treatment policy strategy

Summary measure: Difference in proportions at Week 76

CRR is a composite endpoint derived using several sources of information. Methods for data handling and dealing with missing data for the components of the primary endpoint are provided in Section 4.2.2. Any missing or ambiguous data will be queried, and all efforts will be made to resolve data issues prior to database lock.

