4.2.1.1 Intercurrent Events

The intercurrent events include rescue therapy, treatment failure, study treatment discontinuation, death and early study withdrawal.

Rescue therapy: In some cases of worsening or severely active disease, the investigator may conclude that the patient has failed the randomized treatment regimen and requires rescue therapy.

Two categories of rescue therapies will be considered for the study:

Rescue therapy excluding corticosteroids

Rescue therapies in this category include the following:

Cyclophosphamide

- Anti-CD20 antibodies, including rituximab, ocrelizumab, ofatumumab, and obinutuzumab (if given outside the study protocol)
- Calcineurin inhibitors including ciclosporin, tacrolimus, and voclosporin
- Other investigational, biologic, or targeted therapies used for the treatment of SLE or LN

Patients who receive these rescue therapies will discontinue obinutuzumab or placebo infusions. These patients will continue to be followed according to the study schedule of activities through Week 76 and for at least 12 months from the last dose of obinutuzumab or placebo.

Corticosteroid only rescue

Patients who receive high doses of corticosteroids shortly before the primary endpoint at Week 76 will be considered to have received rescue therapy. Administration of any of the following from Week 64 onward will be considered rescue:

- Methylprednisolone ≥100 mg IV or equivalent
- Prednisone ≥20 mg/day or equivalent (mean dose) over any 2-week period

Any IV or IM corticosteroids will be converted to Methylprednisolone equivalent to evaluate the Methylprednisolone \geq 100 mg IV or equivalent criteria. As for evaluating the prednisone \geq 20 mg/day or equivalent criteria, oral, IV, and IM corticosteroids will be converted to prednisone equivalent dose.

Methylprednisolone pre-medication given prior to obinutuzumab/placebo infusion as per protocol will be exempted from corticosteroid rescue criteria.

Patients who receive corticosteroid rescue will be treated as non-responders. Patients who receive rescue with corticosteroids alone are not required to discontinue obinutuzumab or placebo infusions.

This same rule related to corticosteroid rescue received within 12 weeks prior to endpoint evaluation will also be applied to other secondary and exploratory renal response endpoints (where applicable), including CRR, PRR, ORR, and proteinuric response at Weeks 24, 50, 76, and post Week 76 timepoints.

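### The first key secondary endpoint judges the prednisone taper from oral steroids only, so IV or IM steroid above 7.5 mg/day prednisone-equivalent but below the rescue limits counts as a successful taper

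*SAP*

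**What the plan says.** Protocol 2.1.2, repeated in 6.3.2.1, adds one condition to CRR at Week 76: "No receipt of prednisone > 7.5 mg/day (or equivalent) from Week 64 through Week 76". It names no route.

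SAP 4.3.1.2 keeps that wording in the definition, then adds a restriction: "Only oral corticosteroid will be considered for evaluating the no receipt of prednisone" above 7.5 mg/day. SAP Appendix 1, which records changes to protocol-planned analyses, lists only changed visits for three exploratory response endpoints.

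The endpoint "is defined as achievement of CRR (defined as Section 4.2.1) at Week 76 with the following" condition, and CRR in SAP 4.2.1 requires "No occurrence of rescue therapy, treatment failure, death, or early study withdrawal". From Week 64 onward, SAP 4.2.1.1 counts either of two things as corticosteroid rescue: "Methylprednisolone ≥100 mg IV or equivalent", or a mean of at least 20 mg/day prednisone-equivalent over any two weeks. For the second limit, "oral, IV, and IM corticosteroids will be converted to prednisone equivalent dose". Protocol premedication is exempt from rescue.

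For oral records with a missing daily dose, SAP 4.3.1.2 says "then the dose will be imputed using the dose from the previous dose". The same section says that unresolved data will be handled conservatively.

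**The concern.** Two rules cover the same twelve weeks and the same drug class, but they count different routes. IV or IM steroid below the rescue limits is not rescue, and because it is not oral it is not a taper failure either. Route alone can then decide whether a patient is a success on an endpoint meant to show response on low-dose steroid.

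The endpoint's position raises the stakes. Under SAP 2.1.1 it is tested directly after the primary endpoint at two-sided 0.05. If it fails, the five later key secondary endpoints are all deemed non-significant. An endpoint with that role should measure what its protocol definition says.

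**Working it through.** **The plan's own figure.** The documents give no power for the taper endpoint. The only stated figure is about 90% for CRR (Protocol 6.1, SAP 2.2: 30% vs 50%, 126 per arm, two-sided 0.05). It reproduces with a pooled normal approximation:
- SE under the null = √(2 × 0.40 × 0.60 / 126) = 0.0617
- SE under the alternative = √((0.30 × 0.70 + 0.50 × 0.50) / 126) = 0.0604
- z = (0.20 − 1.96 × 0.0617) / 0.0604 = 1.31, so power = 0.905

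This figure is not in dispute.

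**Inputs for the gap.**
- Protocol Appendix 4: methylprednisolone 4 mg = prednisone 5 mg, a factor of 1.25.
- Protocol 4.3.2.1, Table 2: planned oral dose 5 mg/day in Weeks 24-80.
- Rescue limits: as in SAP 4.2.1.1.

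**Formula.** Two-week all-route mean = (1.25 × total IV/IM methylprednisolone in mg + 14 × daily oral prednisone in mg) / 14. The mean is used only to test the rescue limit. The taper criterion is read as a daily limit. MP = methylprednisolone; a taper pass counts as a success only if the rest of CRR is met.

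| Steroid over 14 days | Two-week mean (mg/day) | Rescue? | Taper, SAP rule | Taper, all routes |
|---|---|---|---|---|
| Oral prednisone 15 mg/day | 15.0 | No | Fail | Fail |
| IV MP 12 mg/day, no oral | (1.25 × 168)/14 = 15.0 | No | Pass | Fail |
| One 80 mg MP + oral 5 | (100 + 70)/14 = 12.1 | No | Pass | Fail |
| One 99 mg MP + oral 5 | (123.75 + 70)/14 = 13.8 | No | Pass | Fail |
| Two 80 mg MP, no oral | 200/14 = 14.3 | No | Pass | Fail |
| Two 80 mg MP + oral 5 | (200 + 70)/14 = 19.3 | No | Pass | Fail |
| Two 99 mg MP + oral 5 | (247.5 + 70)/14 = 22.7 | Yes | Non-responder | Non-responder |
| Three 80 mg MP + oral 5 | (300 + 70)/14 = 26.4 | Yes | Non-responder | Non-responder |

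Any single IV or IM dose of 100 mg methylprednisolone-equivalent or more (125 mg prednisone-equivalent) is rescue.

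**Upper edge of the band.** With 5 mg/day oral, the mean reaches 20 when IV/IM steroid reaches 20 × 14 − 70 = 210 mg prednisone-equivalent in 14 days, or 210/1.25 = 168 mg methylprednisolone. With no oral dose the edge is 280/1.25 = 224 mg.

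**Premedication.** Blinded infusions are at Weeks 50 and 52, then Week 80, so none is scheduled in Weeks 64-76. The exploratory version starts at Week 52, when 80 mg IV methylprednisolone (100 mg prednisone-equivalent) is mandated. That version needs the exemption.

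**Illustration of reach.** No rate of IV/IM use is given. Assume 0-10% of responders per arm would be reclassified, and use the CRR planning rates as a stand-in:
- 5% in both arms gives 28.5% vs 47.5%, power 0.88.
- 10% in the obinutuzumab arm only gives 45% vs 30%, power 0.69.
- 10% in the placebo arm only gives 27% vs 50%, power 0.97.

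The effect could go either way.

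**Missing oral dose.** Carry-forward is conservative when doses are falling. In Weeks 24-80 the planned dose is flat at 5 mg, and SAP 4.3.1.2 itself expects restarts for increased disease activity. A new record with a missing dose may therefore be an increase, which carry-forward replaces with the earlier, lower dose. The adjacent rule for overlapping intervals does the opposite and takes the higher dose.

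**The case against.** The strongest defence is that this is a prednisone taper. Protocol 4.3.2.1 treats IV and oral steroids under separate headings, puts the taper schedule under the oral one, and allows substitution by an equivalent oral steroid. On that reading the SAP clarifies the definition and does not change it. The reading is possible, so the protocol text is not flatly contradicted. It does not close the gap. The SAP reads the same equivalence wording as all-route for rescue, and Protocol Appendix 5 lets IV steroid in equivalent doses temporarily replace oral treatment of a flare when gastrointestinal involvement precludes it. The IV example at 15 mg/day is that substitution.

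Premedication could justify an oral-only rule for the Week 52-76 version, but an explicit exemption does the same job.

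A reader might infer that patients on high-dose IV or IM steroids are generally scored as taper successes. The documents do not support this: the rescue rule inside CRR makes pulse and sustained high dosing non-response. A reader might also set 19.3 against 7.5 as a multiple of the limit, but that compares a two-week mean with a daily limit. A regimen repeated just under the rescue limits for all twelve weeks is a theoretical edge, and nothing in the documents suggests that it occurs.

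A reader might infer bias towards obinutuzumab. None is shown: the rule is the same in both blinded arms. It also stands that IV use is strongly discouraged (Protocol 4.3.2.1), that steroid data are monitored and queried, and that cumulative corticosteroid dose is a separate exploratory endpoint.

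**Conclusion.** The concern holds in bounded form. In Weeks 64-76, IV or IM steroid above 7.5 mg/day prednisone-equivalent passes the taper criterion if each dose is below 100 mg methylprednisolone-equivalent and the all-route two-week mean is below 20 mg/day. The same exposure given orally fails. The SAP gives no reason for the restriction and does not list it as a change.

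The number of patients in the band cannot be derived from the documents and is probably small. The direction by arm is unknown. The conclusion rests on reading the criterion as a daily limit and on the Appendix 4 conversion. It is worth correcting because the endpoint gates five others, not because a large effect is expected. The sample size and the 90% power for CRR are unaffected.

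The missing-dose point is secondary: the rule does not reliably deliver the conservative handling that the SAP promises.

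**What to change.** In SAP 4.3.1.2, and for the exploratory Week 52-76 version, count oral, IV and IM corticosteroids against the daily 7.5 mg limit. Convert doses by Protocol Appendix 4, assign each IV or IM dose to its day of administration, and exclude protocol premedication.

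If the oral-only rule is kept as the main analysis, list and justify it in SAP Appendix 1 and add the all-route version as a sensitivity analysis.

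For an unresolved missing oral dose, use the larger of the preceding and following recorded doses. The reach of this is limited: if both neighbouring records are 5 mg, the result is still 5 mg.

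The cost is a few SAP sentences. The conversion is already specified for rescue, but the assignment of IM doses to days is new and must be stated, since the rescue rule works on single doses and two-week means. A few patients may become non-responders. The change should be made before database lock.
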